The COPE Questionnaire (Carver, Scheier et al. 1989) is a multidimensional coping inventory that assesses the different ways in which people respond to stress. It is a 53-item self-report measure that assesses 14 coping strategies categorized into three coping styles (Problem Focused Coping; Emotion Focused Coping; Less-Useful Coping). While most previously developed coping scales have lacked good empirical validation, the COPE questionnaire has been developed with good overall reliability and construct validity, and is judged as an adequate measure of coping strategies (Parker & Endler, 1992). In this study we will assess stress-related coping at baseline and once during treatment and at the follow-up to assess effects of study medication on stress-related coping.

Cognitive assessments

CANTAB (Cambridge Cognition, Inc) Battery will be administered at baseline (first week of study enrollment) and again at some point during pregnenolone treatment. All CANTAB tasks incorporate testing modes suitable for use across multiple time-points and are presented on a touch-screen computer.

Stroop Color Word Test (Golden, 1976). On the initial trial participants are given 45 seconds to read as quickly as possible a list of 100 color words (red, green, blue) randomly arranged and printed in black ink. On the second trial participants have 45 seconds to identify as quickly as possible the color of 100 "XXXX" printed in either red, green or blue ink. The final trial consists of the 100 words presented in the initial trial in the colors presented in the second trial. In all cases, the word (i.e. red) is different from the color it is printed in (i.e. blue. (e.g. "red"). Subjects are given 45 seconds to name the color of the ink as quickly as possible. The number of raw items read for each trial is recorded and converted to standardized T scores. (5 mins)

Safety and Side Effects Measures

The following safety measures will be assessed at each contact with the patient:

Sitting vital signs: including heart rate, systolic and diastolic blood pressure will be assessed every 15-30 minutes for one hour 2x weekly throughout study. Laboratory chemistry will be assessed at week 2, 5 and week 7 after initial assessment for abnormal values.

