A Systematic Assessment of Treatment Emergent Events (SAFTEE) will be assessed at each visit to assess any adverse events of side effects that may have occurred in patients during the treatment study. The scale will assess physical or health problems since the last visit, including changes in physical appearance and changes in functioning due to physical condition. If the subject describes any changes a detailed assessment of the symptom or complaint will be conducted using the SAFTEE form pages 2-4. An adverse events form developed by our group will be completed for the event according to the criteria outlined in the Data Safety Monitoring Plan in the Human Subjects section. Thus, study staff and investigators will evaluate all adverse events, and an adverse event report will be completed and the Yale HIC and the Data Safety Monitor will be notified (see Data Safety Monitoring Plan for procedures for safety monitoring and reporting of adverse events). Adverse events/side effects will be assessed weekly throughout the study.

Other Relevant Measures:

QMI Vividness of Imagery Scale (Sheehan, 1967) will be used to assess the vividness of mental imagery. The 35 items of the QMI are statements regarding the imagery ability in seven different sensory modalities (visual, auditory, olfactory, cutaneous, kinaesthetic, gustatory, and organic). Subjects are asked to rate their imagery vividness on a 7-point scale (1 = I perceive it perfectly clearly, as if it were real; 7 = I think about it, but I cannot imagine it). A low score on the QMI indicates more vivid imagery.

The Menstrual Cycle Questionnaire (MCQ) is a 30-item standardized instrument including 23 questions about symptoms experienced during a typical menstrual cycle and questions regarding typical cycle and period length. Female subjects will complete the questionnaire at baseline.

4. Genetic Testing N/A

A. Describe

- i. the types of future research to be conducted using the materials, specifying if immortalization of cell lines, whole exome or genome sequencing, genome wide association studies, or animal studies are planned

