3) [name]., Ph.D., [contact], Email: [contact]; [name] is an Assistant Professor at the Department of Psychiatry at Yale University. He has been PI and Co-I on several NIH funded studies examining neuropsychiatric disorders risk, treatment and the underlying etiology of the illnesses.

The DSMB members will evaluate all Adverse and Serious Adverse Events, and will assist the PI in preparing and sending the pertinent expedited reports to the Yale Human Investigation Committee (HIC)/IRB and the NIAAA PO as outlined below. They will monitor the studies quarterly and review all adverse event sheets completed during that period. Although the proposed clinical trial and laboratory study includes generally safe procedures and we do not foresee termination of the study as a direct consequence of study procedures, if there is a need, the DSMB will assist the PI in making critical decisions regarding a particular patient continuing in a study for safety reasons. The DSMB will also review the summary of all Adverse and Serious Adverse Events, which will be reported annually to the Yale Human Investigation Committee (HIC) and the appropriate NIH Project Officer.

Monitoring and Reporting of All Adverse and Serious Adverse Events (AEs and SAEs): Data on all unanticipated, serious-related Adverse Events occurring during the course of conducting this study will be collected, documented and reported to the Yale HIC. A summary of all AE's will be prepared annually, by the project PI and the Data Safety Monitor and submitted to the Yale HIC. The Yale HIC requires the re-approval of study protocols at least annually and will not re-approve the protocol without such reports.

Adverse Events (AE) will be defined on the basis of the NIDA Guidelines on Data and Safety Monitoring for Intervention Trials. These guidelines define an AE as any reaction, side effect or untoward event that occurs during the course of the clinical trial, whether or not the event is considered related to the study interventions. A new illness, symptom, unfavorable or unintended sign, or worsening of a pre-existing condition or abnormality will be considered an AE. Stable chronic conditions such as diabetes that are present prior to study entry and do not worsen will not be considered AEs. For all NIDA-MDC studies including this one, AEs will include events and symptoms reported by the subjects that are of clinical importance as noted by the study staff.

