Thus, mixed linear models will be used to test the hypotheses for each of the specific aims. In each case, Subjects will be treated as a random effect and Sex, Imagery Condition and Timeperiod will be treated as fixed effects. PROC MIXED in the Statistical Analysis System (SAS, version 9.3) will be used to model the experimental effects. Each of the specific aims and hypotheses are listed below. For the treatment section of the study, Cox Proportional Hazards models will be used to ascertain differences in time to relapse between AUD individuals treated with pregnenolone compared with those treated with placebo. We anticipate that pregnenolone-treated individuals will demonstrate a survival function reflecting an increase in number of days to relapse compared to the placebo group.

Specific Aim #1: *To evaluate the safety/tolerability of 300mg and 500 mg/day of PREG vs PLA in AUD individuals. Hypothesis 1: PREG 300 and 500 mg/day will be found to be safe, well-tolerated and with fewer side effects/adverse events as compared to the PLA group. Statistics to test hypothesis 1 will compare safety and adverse events data using percentages of various side effects and number and type of AE's for the three treatment groups by each week in treatment using PROC MIXED procedures in SAS, but also frequencies of overall AEs compared across the 8-week period.*

Specific Aim #2a: To evaluate PREG dose (PLA, 300 and 500 mg/day) effects on ALLO and on provoked cue- and stress induced craving, HPA responses, anxiety/mood and cognitive flexibility in AUD patients.

Hypothesis 2a: Compared to PLA, PREG will dose dependently increase ALLO levels and also decrease stress and cue-induced alcohol craving, anxiety, normalize HPA axis basal and response levels of Cortisol, ACTH and adrenal sensitivity (Cortisol/ACTH ratio) and improve Stroop cognitive flexibility.

Specific Aim #2b: To assess whether PREG-stimulated ALLO levels mediate its effects on provoked craving, anxiety, mood, HPA axis response and cognitive flexibility in the laboratory component. Hypothesis 2b: Compared to PLA, higher ALLO levels in the PREG dose groups will mediate greater reductions in alcohol craving, anxiety, mood, cognitive flexibility and normalizing of HPA axis measures specified in Hypothesis 2a.

Specific Aim #3a: To determine the efficacy of 8-week PREG doses versus PLA treatment on primary alcohol use outcomes, and secondary outcomes including alcohol craving, anxiety and mood.

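### The SAFTEE, a primary safety outcome, has no scheduled pre-dose reading, and the all-AE total can include drinking-related events that the drug is expected to change

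*Combined protocol and SAP*

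**What the plan says.** Section V.3, Safety and Side Effects Measures, opens with "The following safety measures will be assessed at each contact with the patient". It then says that the SAFTEE "will be assessed at each visit to assess any adverse events of side effects that may have occurred in patients during the treatment study", and on the look-back: "The scale will assess physical or health problems since the last visit". The same paragraph closes with "Adverse events/side effects will be assessed weekly throughout the study", although visits are twice weekly. No SAFTEE before the first dose is described. Other measures do have an early reading: the ASI is given before treatment, and CANTAB, the COPE and the menstrual questionnaire at baseline.

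Section V.11 defines an adverse event (AE) as any untoward event during the trial, "whether or not the event is considered related to the study interventions", and adds: "A new illness, symptom, unfavorable or unintended sign, or worsening of a pre-existing condition or abnormality will be considered an AE". Stable chronic conditions are excluded, symptoms reported by subjects must be of clinical importance in the view of staff, and each event is graded for attribution on five levels from definite to unrelated.

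Section V.12 makes SAFTEE side effects and AEs a primary outcome. Under Specific Aim #1, Hypothesis 1 expects fewer events on pregnenolone than on placebo. The analysis compares percentages of side effects and the number and type of AEs by arm and week, and also "frequencies of overall AEs compared across the 8-week period". It uses neither a baseline nor the attribution grade.

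**The concern.** There are two separate problems.

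**No reference reading.** Judging a symptom as new or worse needs something to compare it with. The SAFTEE has no pre-dose reading, so staff rely on history and recall. At the first on-drug visit, the period since the last visit can include days before dosing. The full dose starts without titration, so that visit is also where early side effects would show. The new-or-worse rule governs AEs, whereas the raw side-effect percentages are compared without it. These patients drink heavily and may be in withdrawal. Restlessness, which Section V.9 reports more often on pregnenolone than on placebo in an earlier trial, is a symptom they could already have.

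**Efficacy inside the safety total.** Nothing in the AE definition excludes intoxication, withdrawal or a detoxification admission. Hypothesis 3a expects less drinking on the drug, so such events may differ by arm because the drug works. A fall in them can offset real side effects in the overall count, or can look like good tolerability when side effects do not differ.

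**Working it through.** The plan gives no event rate, alpha, power or sample-size calculation for safety, so there is no figure to reproduce. The only input from the documents is 30 per arm (3 × 30 = 90). All event rates below are assumptions. Power is exact Fisher power for one dose against placebo, two-sided 0.05.

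**1. Pre-existing symptoms.** Let *pre* be the share with the symptom before dosing, the same in each arm. Let *onset* be new onset among the rest: 5% on placebo, 35% on dose. Let *k* be the share of pre-existing symptoms that is counted anyway.

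Counted rate = k × pre + (1 − pre) × onset.

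Example, pre = 20% and k = 1: placebo 0.20 + 0.80 × 0.05 = 0.24; dose 0.20 + 0.80 × 0.35 = 0.48.

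| pre | k | Placebo | Dose | Risk ratio | Power |
|---|---|---|---|---|---|
| 0 | – | 5% | 35% | 7.0 | 0.788 |
| 20% | 1 (all counted) | 24% | 48% | 2.0 | 0.388 |
| 20% | 0.25 | 9% | 33% | 3.7 | 0.525 |
| 20% | 0 (new onset only) | 4% | 28% | 7.0 | 0.616 |
| 40% | 1 (all counted) | 43% | 61% | 1.4 | 0.209 |
| 40% | 0.25 | 13% | 31% | 2.4 | 0.283 |
| 40% | 0 (new onset only) | 3% | 21% | 7.0 | 0.385 |

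Restricting to patients free of the symptom before dosing (24 or 18 per arm) gives 0.706 or 0.518.

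The rows with k = 1 are the worst case, in which the new-or-worse rule fails every time. Part of the loss from 0.788 remains even at k = 0, because fewer patients can have a new onset. A pre-dose reading recovers only the step from k > 0 to k = 0.

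With no drug effect and the same event rate in both arms (20%, 40% or 60%), the Fisher type I error is 0.022 to 0.026. Equal background does not create a false difference.

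**2. Drinking-related events.** Let *w* be the rate of drinking or withdrawal events and *q* the rate of side effects, independent.

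Any-AE rate = 1 − (1 − w)(1 − q).

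- w = 40% v 20% and q = 10% v 30% (placebo v dose): 1 − 0.6 × 0.9 = 46%; 1 − 0.8 × 0.7 = 44%. The side-effect rate triples, and the overall total is 2 points lower on dose.
- q = 5% v 25%, with w = 40% on placebo: the placebo total is 1 − 0.6 × 0.95 = 43%. On dose, w of 40%, 30%, 24% or 20% gives a total of 55%, 47.5%, 43% or 40%. The net difference is +12, +4.5, 0 or −3 points.
- q = 5% in both arms, w = 40% v 20%: 43% v 1 − 0.8 × 0.95 = 24%. This is an apparent advantage of 19 points with no difference in side effects.

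**The case against.** Much of the protection already exists. The AE definition is limited to new or worsened conditions of clinical importance, detailed SAFTEE follow-up starts only when the subject describes a change, and the PROMIS-29 at screening records anxiety, fatigue, sleep and pain. Looking back to the last visit limits double counting, and only the first on-drug window can reach before dosing. The by-type comparison comes before the overall frequency, so 10% v 30% side effects would still be seen there. The analysis is described as mostly descriptive, and no safety threshold is set.

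All of this stands, and it limits the size of the problem. It does not close the gap. The plan does not link the PROMIS-29 to the AE judgement, and its listed domains do not include restlessness. The raw side-effect percentages fall outside the AE rule. The attribution grade is collected but not used in Section V.12. The instruction to assess at each contact neither names nor excludes a pre-dose contact.

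A reader might infer that pre-existing symptoms bias the safety result towards the drug. The documents do not support that: under randomisation and blinding they are expected equally in each arm, so they dilute, with chance imbalance at 30 per arm. A reader might also infer that the plan counts relapse, intoxication and withdrawal as AEs. It does not say so; this follows only from a broad definition with no exclusion, and staff judgement of clinical importance comes in between. Finally, basing Hypothesis 1 only on events that are not alcohol-related is tempting, but it could remove real drug effects, such as restlessness coded as withdrawal.

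**Conclusion.** The point holds in this limited form. A primary safety outcome has no scheduled pre-dose reading on its own scale, and the planned analysis uses neither a baseline nor the attribution grade. Pre-existing symptoms can weaken the comparison but do not favour an arm. The 39% and 21% power figures are a worst case. If a quarter of pre-existing symptoms are counted, the figures are 53% and 28%, against 62% and 39% with new onset only. The drinking-related problem affects the overall total: a 20-point excess of side effects nets to zero if drinking events fall from 40% to 24%. The by-type comparison partly guards against this. Every rate here is an assumption, as is the independence of drinking events and side effects. The conclusion rests on the missing pre-dose reading and the unused attribution grade, not on these values. The change is worth making before enrolment, because a pre-dose reading cannot be recovered later.

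**What to change.** 1. Complete the SAFTEE once after consent and before the first dose. At the first on-drug visit, ask about the time since the first dose.
2. In Section V.12, analyse side effects and AEs as new or worse than the pre-dose reading.
3. Keep the all-AE total as the stated comparison for Hypothesis 1. Beside it, report AEs by arm by the existing attribution grade, and show alcohol-related events (intoxication, withdrawal, detoxification admission) separately without removing them from the total.
4. Reconcile the SAFTEE frequency in Section V.3 (each visit or weekly), and the number of groups in Section V.12, which refers to two medication groups in its opening paragraph and three treatment groups under Aim 1.

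The cost is one extra checklist at intake, a blinded judgement on which events are alcohol-related, and some extra table rows. Some of those judgements will be uncertain, which is why the total is kept. Reporting of serious events is unchanged.

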3. **Research Plan:** Summarize the study design and research procedures using non-technical language that can be readily understood by someone outside the discipline. **Be sure to distinguish between standard of care vs. research procedures when applicable, and include any flowcharts of visits specifying their individual times and lengths.** Describe the setting in which the research will take place.

1. Study Design and Overview

Ninety treatment seeking men and women with AUD will be recruited to participate in and complete this preliminary study. Participants will be recruited through flyers and advertisements in local newspapers and from community substance abuse treatment facilities. Subjects will participate in an initial screening and intake session to obtain informed consent, followed by physical examination and blood work to determine eligibility. Eligible

participants will be randomly assigned to 2 doses of PREG (300/500 mg/day) vs placebo (PLA) treatment (N=30/group) over 8 weeks. In week 2, AUD patients will participate in a 3day human laboratory study where they will be exposed to three experimental sessions of stress, alcohol cue and neutral-relaxing imagery on separate days (Fox et al.,2007; 2009; Sinha et al., 2008; 2009; 2011). Throughout the study, participants will come twice-weekly to the Yale Stress Center to receive medication, counseling and provide urine samples for UTOX. Women will be enrolled during the mid-luteal phase of the menstrual cycle so that laboratory sessions will be scheduled during the early to mid-follicular phase of the cycle when endogenous sex hormone levels are low prior to ovulation. PREG doses and matching placebo will be obtained by Yale IDS for compounding and dosing to 300mg and 500mg of PREG or PLA. Participants will self-administer study medication on a twice-daily dosing schedule throughout entire study.

Subjects will begin with full respective dose of medication immediately without a titration period, as previous studies with similar doses of pregnenolone up to 500 mg/day at b.i.d. dosing to be well tolerated and with no side effects (Marx et. al., 2009; Marx et al., 2014; Brown et al., 2014; Sripada et al., 2013).

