Once a subject is deemed eligible, signs consent and completes all intake assessments, s/he will be randomized to 300mg PREG, 500mg PREG, or PLA and exposed to three laboratory sessions as close together as possible of guided imagery of stress, drug cues and neutral-relaxing cues in week 2 (identified as lab DAY 1, DAY 2, and DAY 3). In a session prior to laboratory sessions, subjects will participate in an imagery script development to provide descriptions of recent stressful, drug cue related and neutral relaxing situations to the research assistant. On the day before laboratory session 1 , subjects will participate in a relaxation and imagery training and IV habituation session, followed by three laboratory sessions that include IV blood drawing.

Daily surveys using a Smartphone platform (MetricWire) monitoring will prompt subjects to take study medication, and provide responses on their alcohol use, craving, stress and mood states for the day (see below for detailed description).

Genetic studies:

Ten mL of whole blood will be collected during physical examination to assess eligibility, and thirty-two mL of whole blood will be also collected from patients on the day of the first laboratory session (LAB DAY 1) for the purposes of understanding genetic factors that may affect craving.

Throughout the 8 week study, subjects will self-administer 300mg/day, 500mg/day or PLA/day and study staff will provide weekly medication packs to subjects.

Participants will be seen twice per week at the Yale Stress Center at [name] to receive once/week counseling, provide urine and receive contingency management for treatment attendance. Daily surveys using the smartphone platform (MetricWire) monitoring will prompt subjects to take study medication, and provide responses on their alcohol use, craving, stress and mood states for the day. Smartphone data will be collected daily. Subjects will be prompted at two random times in the morning and afternoon to complete a brief 1-minute survey of questions and a third 5-10 minute survey to be completed at night before bedtime. The surveys are set up with standard automated questions and prompts and subjects will use the smartphone key pad to answer the prompts (via MetricWire).

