Microarray profiling will be used to detect these molecular changes by comparing the molecular profile of the blood drawn during the physical to blood samples drawn on day 1 of the laboratory sessions. Total RNA will be isolated from whole blood collected at the indicated times using the PAXgene Blood RNA Isolation kit (QIAGEN, Valencia, CA) per the manufacturer's instructions. Total RNA will be depleted of globin mRNA message using GLOBINclear hybridization capture technology (Ambion, Austin, TX). Globin-reduced total RNA will then be used to carry out cDNA synthesis and overnight in vitro transcription utilizing the Illumina TotalPrep RNA Amplification Kit (Ambion). Biotinylated cRNA (1.5 µg) will be hybridized onto an Illumina Sentrix Beadchip (Human-6v2). This platform was chosen because of its lower cost in relation to Affymetrix GeneChips and demonstrated utility in detecting expression changes in RNA samples derived from whole blood (Barnes et al., 2005). Hybridizations and array scanning will be carried out at the Yale Neuroscience Microarray Center.

5. **Subject Population:** Provide a detailed description of the types of human subjects who will be recruited into this study.

Ninety treatment seeking individuals with current alcohol use disorder (half men; half women) will be recruited to participate in this study. Subjects will be recruited from the community without regard to sex, racial, or ethnic background. We expect a representative sample will be drawn from the community.

6. **Subject classification:** Check off all classifications of subjects that will be specifically recruited for enrollment in the research project. Will subjects who may require additional safeguards or other considerations be enrolled in the study? If so, identify the population of subjects requiring special safeguards and provide a justification for their involvement.

Non-	 Children	 Healthy	 Fetal material, placenta, or	 dead fetus
	 English Speaking	 Prisoners	 Economically	 disadvantaged persons
	 Decisionally Impaired	 Employees	 Pregnant	 women and/or fetuses

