	 Yale Students	 Females	 of childbearing potential	

NOTE: Is this research proposal designed to enroll children who are wards of the state as potential subjects? No Yes If yes, see Instructions section VII #4 for further requirements)

7. Inclusion/Exclusion Criteria: What are the criteria used to determine subject inclusion or exclusion?

A. Human Subjects Involvement, Characteristics and Design

Ninety participants who meet current DSM-V criteria for alcohol use disorder and who are treatment seeking will be recruited to participate in this study. Women will be included in subject sample, and will represent 50% of the study sample in order to explore gender effects. The AUD individuals recruited into our previous studies have tended to be of the following racial and ethnic background: 35% are Caucasian, 60% are African-American, 5% are Hispanic. As a result, we expect that the projected demographics of our sample will follow the above gender and race breakdown. The following inclusion and exclusion criteria will be followed: Inclusion Criteria:

- i. Male or female individuals, ages 18 to 68.
- ii. Subjects must meet current DSM-V criteria for alcohol use disorder; documented positive urine toxicology screen for alcohol at intake or collateral information from family members, significant others, room-mates etc., on recent use.
- iii. Subject has voluntarily given informed consent and signed the informed consent document.
- iv. Able to read English and complete study evaluations.

Exclusion Criteria:

- i. Women who are pregnant, or nursing or are of childbearing potential and not practicing an effective means of birth control.
- ii. Meet current severe criteria for use disorder on another psychoactive substance, such as amphetamines, hallucinogens/PCP, excluding nicotine.
- iii. Meet current criteria for an opiate use disorder, including heroin (assessed via urine toxicology and self report).
- iv. Current use of any psychoactive drugs (urine toxicology), including naltrexone and antabuse, excluding stable use of SSRIs, SNRIs, and benzodiazepines.
- v. Any psychotic disorder or current Axis I psychiatric symptoms requiring specific attention, excluding stable use of SSRIs, SNRIs, and benzodiazepines.

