Data Analytic Procedures: Since patients will be randomly assigned to the pregnenolone doses and placebo treatment groups, we do not expect the groups to be different on demographic, prior drug use history or other predictor variables. Nevertheless, prior to undertaking the specific analyses, we will compare the treatment groups on demographic variables, substance use characteristics and previous psychiatric history/predictor variables using t-tests/chi-square analyses as appropriate. If any group differences are found, the specific variable will be entered as a covariate in all of the specific analyses.

The laboratory study component proposes a 3 X 2 X 3 mixed-factorial design with Treatment (300mg Pregnenolone vs. 500mg Pregnenolone vs. Placebo) and Sex (AUD women vs. men) as the Between-Subjects factors and Imagery Condition (Stress, Drug Cues and Neutral cues) X Time Period 7 (Baseline, Image, Recovery 1, recovery 2, recovery3, Recovery 4 and Recovery 5) as the Within-Subjects factors. Order of imagery conditions will be randomly assigned and counterbalanced across subjects. As measurements for imagery condition and time period will be repeated within subjects, these are not independent, leading to correlations between measurements. Mixed linear models provide a way not only to model the mean differences between levels of factors, but also allows for modeling of the variancecovariance matrices (Laird and Ware 1982) (Littell, Milliken et al. 1996). This is particularly advantageous for designs such as the one proposed here which require repeated laboratory measurements within subjects. Furthermore, these models also have the capacity to handle missing data, without excluding subjects with missing data points (Cnaan et al., 1997; Littell et al., 1996).

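### No described procedure secures the half-women sample or the sex-by-dose cells on which the plan's analysis of sex differences depends

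*Combined protocol and SAP*

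**What the plan says.** **Role of sex.** The Statement of Purpose (Section V.1) lists sex differences across the outcomes as its third element. Data Analytic Procedures (Section V.12) makes Treatment (three levels) and Sex (two levels) the between-subjects factors of the laboratory component and lists Sex as a fixed effect in the mixed models. Gender also appears under the Exploratory Aim.

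**Target.** Section V.5 states: "Ninety treatment seeking individuals with current alcohol use disorder (half men; half women) will be recruited to participate in this study". Section V.7 adds that women "will represent 50% of the study sample in order to explore gender effects".

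**Recruitment.** The next sentences of Section V.5 read "Subjects will be recruited from the community without regard to sex, racial, or ethnic background" and "We expect a representative sample will be drawn from the community". The recruitment parts of Sections V.3 and VII describe no quota, cap or sex-specific step.

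**Assignment.** Study Design and Overview (Section V.3) says "participants will be randomly assigned to 2 doses of PREG (300/500 mg/day) vs placebo (PLA) treatment (N=30/group) over 8 weeks". The laboratory description later in Section V.3 says "s/he will be randomized to 300mg PREG, 500mg PREG, or PLA", and Section V.12 begins a sentence "Since patients will be randomly assigned to the pregnenolone doses and placebo treatment groups". No sequence method, block size or stratification factor is given. The only counterbalancing described concerns the order of the imagery conditions.

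**Imbalance.** Section V.12 compares the groups at baseline with t-tests or chi-square tests and enters a variable as a covariate if a difference is found.

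**The concern.** The plan commits to a sex-balanced sample and to an analysis that crosses sex with dose, but the procedures it describes would produce that balance only by chance. Two things are unprotected: the total number of women, and their spread over the three arms.

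Other rules bear on women alone. Enrolment is timed to the menstrual cycle (Section V.3), and pregnancy, nursing and contraception form an exclusion criterion (Section V.7). Section V.7 cites earlier studies for the expected racial and ethnic mix but gives no past share of women, so nothing shows that half would be reached unaided.

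At stake is the precision of the sex-specific dose estimates, which depends on the smallest cells. In the treatment phase there is also the question of whether a chance sex difference between arms would be adjusted for. The Cox model and the non-parametric tests of alcohol use in Section V.12 name no sex term.

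**Working it through.** **Inputs from the documents:** N = 90, three arms of 30, half women. Alpha, power, effect size and SD are not stated, so there is no sample-size calculation to reproduce. The arm arithmetic agrees: 3 × 30 = 90. The implied cell size is 90 / 6 = 15; the documents do not state it.

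**Assumptions:** the share of women among eligible recruits (range shown); two-sided alpha 0.05 and 80% power.

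**1. Recruitment without a quota.** The number of women is Binomial(90, p).

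| Share p (assumed) | Expected women | 95% range | Chance of at least 45 |
|---|---|---|---|
| 0.50 | 45 | 36 to 54 | 54% |
| 0.40 | 36 | 27 to 45 | 3.5% |
| 0.30 | 27 | 19 to 36 | below 0.01% |
| 0.25 | 22.5 | 15 to 31 | below 0.01% |

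Even at p = 0.50, the total falls between 43 and 47 in only 40% of trials.

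**2. Precision of the sex-by-dose contrast.** For one dose against placebo, women against men, the variance is proportional to the sum of 1/n over four cells. At 15 per cell this is 4/15 = 0.267.

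- 36 women, split evenly (12 and 18 per arm): 2/12 + 2/18 = 0.278, ratio 1.04.
- 27 women, split evenly (9 and 21 per arm): 2/9 + 2/21 = 0.317, ratio 1.19.

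Adding chance spread over arms of 30 without stratification (200,000 simulated draws), the mean ratio is 1.07 for 36 women and 1.25 for 27 women. The median smallest cell is 10 and 7 respectively.

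**3. Missing stratification alone, with 45 women and 30 per arm.** Women per arm are hypergeometric with mean 15 and variance 30 × 0.5 × 0.5 × 60/89 = 5.06, so SD 2.25 and 95% range 11 to 19. In the same simulation:

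- all three arms split 15/15 in 3.6% of trials;
- the smallest of the six cells has median 12, and is 10 or fewer in about 11% of trials;
- the contrast variance rises 2.4% on average (95th percentile 7.7%). The average rise widens the standard error by about 1.2%, since √1.024 = 1.012.

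**4. The covariate rule.** Suppose the arms contain 11, 15 and 19 women. Each of four cells deviates by 4 from an expected 15, so chi-square = 4 × 16/15 = 4.27. Across three groups (2 df), p = exp(−4.27/2) = 0.12. Between the two extreme arms (1 df), p = 0.039. Whether sex enters the models would therefore depend on which test is run, and the plan does not say.

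**5. What full balance buys.** The detectable effect is (1.960 + 0.842) × √(sum of 1/n):

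- sex-by-dose contrast at 15 per cell: 2.802 × √(4/15) = 1.45 SD;
- one dose against placebo within one sex: 2.802 × √(2/15) = 1.02 SD;
- one dose against placebo, whole arms: 2.802 × √(2/30) = 0.72 SD.

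At 9 women and 21 men per arm, the first figure becomes 2.802 × √0.317 = 1.58 SD.

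**The case against.** The recruitment sentence may be ordinary non-discrimination wording in a review-board form. It stands directly after an explicit half-and-half target that Section V.7 repeats. That reading is fair, but it leaves the target without a mechanism.

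A reader might infer that assignment is unstratified. The documents do not say so; they are silent on the method. Nor can a protocol show that the cells were not achieved, only that nothing described secures them. A reader might also apply simple-randomization probabilities, under which some arm would have 10 or fewer of 45 women in 22% of trials and an arm of 25 or fewer would occur in 46%. Those figures fit poorly with the stated 30 per group. With arms fixed at 30, the first falls to 6.5%.

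The claim that dose would be confounded with sex is also too strong. Sex is a factor in the laboratory mixed models, which tolerate unequal cells, and the covariate rule may add it elsewhere. The sentence listing fixed effects is worded to cover every aim, but it also lists imagery condition, which exists only in the laboratory. The Cox and non-parametric treatment-phase analyses still name no sex term.

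Finally, this is a preliminary study meant mainly for description and effect-size estimation, gender sits in the Exploratory Aim, and no numbered hypothesis concerns sex. This stands, and it limits the weight of the point. It does not remove the gap, because sex differences are also in the stated purpose and in the factorial design.

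**Conclusion.** The concern holds in a limited form. The 50% target and the implied 15 per cell have no described procedure behind them.

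The recruitment rule carries most of the risk. Its size rests on an assumed share of women: the average rise in contrast variance is about 7% with 36 women and about 25% with 27. If 45 women enrol and the arms are fixed at 30, missing stratification by itself is a minor loss, about 2.4% in variance on average, with an uncomfortably small cell in roughly one trial in nine.

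The improvement is worth making because it costs little, but the gain is modest. Balanced cells would still leave the sex-by-dose test able to detect only about 1.45 SD under the assumed alpha and power.

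**What to change.** 1. **Randomization (Section V.3).** Specify permuted blocks stratified by sex, with block sizes in multiples of three that close at 45 per sex. This gives 15 per cell at randomization, or about 13.8 (15 × 0.92) if the 92% completion rate cited from earlier studies were repeated.
2. **Recruitment (Section V.5).** Reconcile the recruitment sentence with the target. Say that enrolment will be tracked to 45 men and 45 women, and how.
3. **Analysis (Section V.12).** Name sex as a prespecified factor in all efficacy models, including the Cox and alcohol-use analyses of the treatment phase, whatever a baseline test shows. For alcohol use, this calls for a model or stratified test that can carry a sex term.
4. **Status.** Label the sex-by-dose analysis exploratory and report estimates with confidence intervals.

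The cost is one stratified list at the pharmacy, an enrolment tally and a few lines of text. The downside is that some late volunteers of the commoner sex may be turned away, or recruitment may slow.
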